## 9.0 Incomplete Disclosure or Deception:

There is no deception involved in this study. Participants will be made aware that they will be randomized to one of two therapies.

## 10.0 Recruitment Methods:

Participants will be recruited by research coordinators through the IPHP. If an IPHP clinician identifies a patient as meeting the eligibility criteria, a research coordinator will

be called in to speak with the participant about the study. Coordinators will follow a recruitment script. In addition, recruitment flyers and postcards will be placed in the waiting area of the IPHP, and will be shared with IPHP clinicians.

#### **11.0 Consent Process:**

The consent process will be carried out by the research coordinators at the IPHP. Written informed consent including HIPAA authorization will be obtained at same visit as screening and determination of eligibility. All participants will be asked about their understanding of their participation, and will have an opportunity to ask questions about the study prior to agreeing to participate. Participants will be free to consult with others (e.g., family members) prior to providing informed consent. Participants will provide written informed consent before beginning the study. Participants will be informed that they are free to withdraw from the study at any time without consequence. Ongoing consent will not be formally assessed after participants provide informed consent, but research team members will be trained to discuss any questions that may arise and what to do if a participant chooses to withdraw from the study. See consent form attachment.

#### **12.0 Financial Compensation:**

Each participant, irrespective of treatment group, will be compensated \$100. Participant payment will occur in three blocks: once they have completed the 12 therapy sessions they will receive \$70 total (\$5 per session, with a \$10 bonus for completing all 12 sessions), then they will receive an additional \$15 for each follow-up assessment. Compensation will be prorated to \$5 per session completed if the participant withdraws from the study. Payments will be provided in the form of a Stored Value Card (Visa) for therapy sessions and via virtual gift card for online follow-up surveys. If a participant withdraws from the study they will be given the option to receive their pro-rated payment either via Stored Value Card or virtual gift card based on their preference.

#### **13.0 Audio Recording:**

Audio recording of therapy sessions will be optional. For participants that provide consent for audio recordings, therapy sessions will be audio recorded to be reviewed later by the principal investigator, to ensure fidelity of treatment and for supervision of therapists. Recording devices will be stored in a locked cabinet in [name] lab space. [name] and the study therapists will have keys to the cabinet. Study therapists will be required to return the recording devices to the cabinet directly after completing sessions for the day. Recordings will be destroyed one year after study completion.

#### **14.0 Potential Benefits to Participants:**

Participants will not necessarily benefit from taking part in this research. However, possible benefits include: 1) We can improve behavioral treatment for patients with lower urinary tract symptoms and comorbid emotional distress. 2) This study will provide important information about the causal link between emotional distress and urinary symptoms. 3) Participants may directly experience a reduction in their urinary symptoms and emotional distress. The potential benefits of this study should outweigh the risk to individual participants.

## **15.0 Risks to Participants:**

Participating in this study involves minimal risks. It is possible that participants may feel some shame, emotional discomfort, distress, boredom/fatigue when completing the assessments of urinary symptoms, depression, and anxiety, or when participating in therapy. If we find that participants in the study are at risk for harming themselves or others, we will follow the protocol to connect the participant with crisis services, and document the situation accordingly. We will inform participants that their participation in this study may result in a loss of privacy. This includes data from questionnaires entered into a computerized database, questionnaires completed online, as well as written therapy notes. Several steps will be taken to protect confidentiality and minimize the above risks.

If a participant withdraws from any part of the study (e.g., does not complete one of the surveys), they are welcome to participate in other aspects of the study. If a participant chooses to withdraw from the study, data that has been collected during their participation will be analyzed unless the participant specifies otherwise.

## **16.0 Provisions to Protect the Privacy and Confidentiality of Participants and the Research Data:**

Participants will provide written informed consent. Participants will be given a copy of the consent materials for their records. To protect confidentiality, participants will not be identified by name, but by a unique participant identification number. The key linking participant name to identification number will be stored in a password-protected file. Any other identifying information (e.g., contact information) will be kept separate from the research data. All information, data, and recordings will be kept in secure, password-protected files. Any physical data and forms (e.g., consent) will be kept in a locked cabinet in a locked room. We will inform participants that unless required by law, only the research team and representatives of the Institutional Review Board have the authority to review any study records. All parties with access to the data will be required to maintain confidentiality. Using trained graduate students as therapists will ensure that any potential safety issues are identified and referred to appropriate services. Further, therapists will be supervised by a licensed clinical psychologist. All members of the research team will complete the ethics courses required by Northwestern, including the CITI web-based course on human subjects protection.

## **17.0 Data Monitoring Plan to Ensure the Safety of Participants:**

### **17.1 Data Monitoring**

Each participant will be assigned an anonymous study identification number, which will be used on all study forms. A list of participant names with study IDs will be kept in a secure location separate from study materials. Participants will respond to questionnaires on tablets with a link from REDcap, but have the option to respond on paper forms if preferred, for baseline, mid-treatment, and posttreatment assessments. All paper forms will be de-identified and stored in locked storage using only study ID numbers. After the study visits where measures are given, for any surveys completed on paper the study coordinators will copy the data into REDCap. Subject name, date of birth, and copy of consent will be

entered into StudyTracker. Follow-up assessments will be completed online and connected to REDCap. Data exported from REDCap in a spreadsheet will be stored on the department shared drive (FSMFiles), where only study personnel have access. The spreadsheet will be shared between the study team via their shared drive access, REDCap access, Box.com access, or if necessary secured @northwestern email accounts. The research team will assure complete protection of all data behind Northwestern University's firewalls.

Participants will meet with a therapist on a weekly basis. Any adverse events discussed in therapy will be reported to principal investigators to determine whether the event is study related and if further assessment is needed. Moreover, at the end of the study, each participant will receive a list of referrals for therapy if they would like or need further treatment. [name] is a licensed clinical psychologist; he can assist in connecting participants with a therapist if needed.

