#### **4.0 Sample Size:**

This study will include up to 40 participants. UP-CBT has been shown to have quite large effects (Cohen's  $d$  values of 1.7 or greater). For this study, we have chosen a slightly more conservative estimate for Cohen's  $d$  of 1.5, which represents 1.5 standard deviations between the treatment effect of UP-CBT versus the control group. Based on a power analysis, we would require 16 women per group, in the data analyzed, to detect a treatment effect with  $> 98\%$  power with a Type I error rate of  $\alpha = .05$ , two-tailed. Study withdrawal is estimated at roughly 20%, leaving an estimated final sample of 32 participants for data analysis (see CONSORT diagram below).

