### 8.3 Measures

Participants will be asked to complete questionnaires at baseline, mid-treatment (after 6 sessions), posttreatment (after 12 sessions), at a 3-month follow-up, and at a 6-month follow-up. Baseline, mid-treatment, and posttreatment assessments will be completed on tablets with a link from REDcap, though participants will have the option to

respond on paper forms. Both follow-up assessments will be carried out online with a link sent via email. The primary outcome tool for this study will be the six-item Urinary Distress Inventory (UDI-6), which is a subscale of the Pelvic Floor Distress Inventory (PFDI), as measure of urinary symptoms. We will also measure anxiety using a short form from the NIH Patient Reported Outcomes Measurement Information System (PROMIS), which has been shown to be reliable and valid; this form is brief and easy to complete. Secondary measures include the PROMIS profile (depression, fatigue, pain, physical function, sleep disturbance, and social roles), trauma history assessed with the PTSD Checklist for DSM-5 with Life Events Checklist (PCL-5), the Mini-IPIP, a 20-item short form of the International Personality Item Pool measure of the Big Five personality traits, the Ruminative Responses Scale (RRS) short form, and the Patient Global Impression of Improvement (PGI-I) – a one item self-report assessment of improvement of urinary symptoms. In addition, at both follow-up assessments, participants will be asked whether they have received any treatment outside of the study for their urinary symptoms and/or their anxiety. Any treatment participants receive outside of the study will be tracked in this manner and included in data analyses.

Table 2. Timing of Assessments

Measure	Estimated Completion Time	Baseline	Session 6	Session 12	3 Month Post-Treatment Follow-up	6 Month Post-Treatment Follow-up
Medical history and physical exam	0 (part of regular medical visit and extracted from EMR)	X				
Demographic questionnaire	1 min	X				
Single Item Literacy Screener (SILS)	< 1 min	X				
Brief Medication Questionnaire (BMQ) 	3-5 min	X			X	X
Primary outcome 1: PROMIS Anxiety subscale of profile (4 of 29 items below)	See below for entire profile	X	X	X	X	X
Primary outcome 2: Urinary symptoms using the Urinary Distress Inventory (UDI-6) of the Pelvic Floor Distress Inventory (PFDI)	1-3 min	X	X	X	X	X

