#### 8.4 Therapy

Participants will be scheduled to come to an individual treatment session once per week for 12 weeks, at a convenient time for them, on the Northwestern Campus. This arrangement allows for a one-stop experience for the patient, maximizing their convenience. As described above, participants will be randomized to one of two therapy conditions: UP-CBT or supportive therapy. All sessions, in both conditions, will be 45 minutes in duration. If a participant happens to miss or cancel a session they will be rescheduled.

Unified-Protocol Cognitive Behavior Therapy (UP-CBT) is a form of therapy that draws upon various forms of cognitive-behavior therapy to “unify” the most important tools into one protocol. Cognitive-behavior therapy has been a leading treatment for depression and anxiety for decades, but historically has focused on specific disorders (e.g., major depression, social anxiety disorder, panic disorder). UP-CBT includes a variety of general-purpose techniques to help people cope more skillfully with emotionally stressful situations. This includes dealing with emotional situations by reappraising negative thoughts (e.g., “If I get nervous at work, the stress I feel will be temporary and won’t kill me” rather than “I can’t deal with my life”). UP-CBT focuses on dealing with stress in general, but its techniques are readily adaptable to dealing with urinary symptoms. For example, a woman might have catastrophic thinking about urine leakage (“What if someone notices that I’ve leaked?”). These catastrophic thoughts can result in strong fear responses, as well as potentially problematic behaviors (e.g., avoidance of social situations or even skipping work). In general, UP-CBT teaches people to track emotions, thoughts, and behavior in an effort to identify maladaptive patterns. In addition, participants learn to restructure their thoughts, and to more confidently confront situations that they find challenging. Towards the end of treatment, patients learn to prevent relapses through practice of therapy skills. Participants in the UP-CBT group will be asked to complete homework outside of the therapy session, to practice therapy skills. Homework will be completed in their therapy workbook, and they will be instructed to bring their workbook to each session. After completing the 12 sessions, participants will be able to keep their workbook.

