Supportive therapy is a non-active form of psychotherapy that has been widely used as a control condition in therapy studies. Many of the elements of supportive therapy may be beneficial to some participants, just as pill placebos benefit some participants in drug trials. As such, it is an excellent control condition because it is not merely “sham

therapy". Supportive therapy is widely-used in clinical community settings. In this condition, no cognitive-behavioral exercises will be used. Supportive Therapy allows for careful control over the number of therapy sessions and time per session. Thus, it is ideal for being able to match to UP-CBT. The protocol for supportive therapy will include 1) education about urinary symptoms, anxiety, and depression, 2) discussion of patient goals, 3) sharing of concerns in a nonjudgmental environment, 4) discussion of the possible connections between urinary symptoms and emotional distress, and 5) reflective listening. Participants in supportive therapy will *not* be given homework.

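### Section 17.1 provides for reporting adverse events only when they come up in therapy, so there is no general adverse-event collection after session 12 or after a woman stops attending.

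*Combined protocol and SAP*

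**What the plan says.** Section 17.1 (Data Monitoring) introduces safety reporting with "Participants will meet with a therapist on a weekly basis" and then states the rule: "Any adverse events discussed in therapy will be reported to principal investigators to determine whether the event is study related". It adds that every woman gets a list of therapy referrals when the study ends. Section 16.0 likewise relies on the therapists to pick up safety problems.

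Section 8.4 sets the length of that contact: "Participants will be scheduled to come to an individual treatment session once per week for 12 weeks". Section 8.3 sets the later assessments: "posttreatment (after 12 sessions), at a 3-month follow-up, and at a 6-month follow-up". Of the last two it says "Both follow-up assessments will be carried out online with a link sent via email".

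Table 2 lists what is collected at 3 and 6 months: the medication questionnaire, the PROMIS profile (including anxiety), UDI-6, PGI-I and the follow-up treatment questions. Section 8.3 describes the last of these: "participants will be asked whether they have received any treatment outside of the study for their urinary symptoms and/or their anxiety". No adverse-event item appears in any column of the table.

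Section 17.2, to which section 15.0 points, is a separate procedure for women who report thoughts of harming themselves or others. Section 15.0 also lets a woman who withdraws from one part of the study continue with the rest.

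**The concern.** Section 17.1 ties general adverse-event reporting to a conversation in a session. When the sessions end, so does the only general route the plan describes. A woman who stops therapy because it distressed her leaves that route at the moment her experience is most relevant, and no exit question is planned.

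The plan makes statements that such data would be needed to check. Section 15.0 foresees shame, discomfort and distress from both the questionnaires and the therapy. Section 3.1 asks women to put off usual urinary treatment and asserts that the wait does no harm. Section 14.0 says the benefits should outweigh the risk to the individual. With no definition of an adverse event, no standard question and no collection window, the trial would have little to report on any of these.

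There is also a question of comparability. Within therapy, a report depends on the woman raising the matter unprompted and on a therapist, who necessarily knows the arm, passing it on. Session content differs by design. Supportive therapy includes "sharing of concerns in a nonjudgmental environment" and reflective listening, while UP-CBT is a skills programme with a workbook and homework.

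**Working it through.** No sample-size or power figure in the plan bears on this point, so there is none to reproduce. The check is a comparison of sections and a short calculation of time covered.

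**Routes by which an adverse event could be recorded**

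| Possible route | What the plan provides | Open after session 12? |
|---|---|---|
| Mention in a session (17.1) | Therapist reports to the principal investigators | No; sessions have ended |
| Question on a scheduled form (Table 2) | None at baseline, session 6, session 12, 3 months or 6 months | No |
| Session progress notes (8.4.1) | Written after each session for research use; no adverse-event field described | No |
| Risk protocol (15.0, 17.2) | Thoughts of harm to self or others only; therapist carries out the steps | Not worded as limited to sessions, but nobody is named to act on an online disclosure |
| Outcome, medication and outside-treatment forms (8.3, Table 2) | Collected at 3 and 6 months | Yes, but no safety review and no recording as adverse events |
| Analysis (8.5) | No adverse-event summary | Not applicable |

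**Time covered for a woman who completes therapy**

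- Therapy: 12 weeks (section 8.4).
- Follow-up: 6 months after treatment (section 8.3), taken as 6 × 52/12 = 26 weeks.
- Total participation: 12 + 26 = 38 weeks.
- With the section 17.1 route: 12/38 = 32%.
- Without it: 26/38 = 68%.

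Section 8.4 says missed sessions are rescheduled. That would lengthen the therapy period and lower the 68% somewhat.

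**Time covered for a woman who stops early**

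If her last session falls in week k, the share of the planned 38 weeks without the route is (38 − k)/38. As an illustration, stopping after session 6 gives (38 − 6)/38 = 32/38 = 84%. The documents do not say how many women will stop sessions or when, so this cannot be turned into a figure for the whole trial.

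**Capture by arm**

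Sections 8.4 and 17.1 together establish three facts: reports are unsolicited, they pass through the treating therapist, and session content differs. They also establish one fact on the other side: the arms are matched on number and length of sessions. Nothing in the documents gives an elicitation rate for either arm, so neither the size nor the direction of a difference can be calculated.

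**The case against.** Several parts of the case for the plan as it stands are sound.

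- **Women are still followed.** A reader might infer that women are unmonitored after session 12. The documents do not support that. Anxiety, the full PROMIS profile, UDI-6, PGI-I, medication and outside treatment are all collected at 3 and 6 months, and a woman who stops therapy may still complete these forms. They cover much of the ground where section 15.0 expects difficulty. What remains is narrower: no adverse-event question is asked, and nobody is assigned to read the answers for safety.
- **A second route exists for the gravest events.** The triggers in sections 15.0 and 17.2 are not confined to sessions. This stands, though the scope is limited to harm to self or others and the steps fall to the therapist.
- **Withdrawal is not stopping therapy.** A reader might apply "Study withdrawal is estimated at roughly 20" per cent (section 4.0) to count the women who lose the route early. That figure is withdrawal from the study, and section 15.0 separates leaving one part from leaving altogether. The count cannot be derived from it. Nor do the documents say that women who stop are the most distressed.
- **Bias between arms is not shown.** A reader might infer that supportive therapy will draw out more events. UP-CBT trains women to track their emotions, thoughts and behaviour, which could prompt as much disclosure or more. Only the possibility of a difference stands.
- **The trial has no comparative safety aim.** It is a pilot of up to 40 women with risks described as minimal, and neither the aims nor section 8.5 mentions a harms comparison. Better collection would not make so small a trial informative about differences in harm. This argues for a light method and descriptive reporting, but not for leaving most of participation without a question.
- **Section 17.1 does not say that other events will be ignored, and some pages were withheld from the text available.** Both are true, so the finding is limited to what can be read. The data-monitoring section itself is present.

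**Conclusion.** The concern holds in a limited form. As written, the plan has no general adverse-event collection for about 26 of 38 weeks (68%) in a woman who completes therapy, and for a larger share in one who stops attending. This rests on reading 6 months as 26 weeks, on therapy lasting 12 weeks, and on the visible text being complete on this subject. The possibility that capture differs between arms is a reasonable inference from how reports arise; its direction and size are unknown, and the finding does not depend on it. No primary endpoint, sample-size figure or power figure is affected. This is an inexpensive improvement in safety ascertainment that should be made. It is not a flaw that threatens the trial's main conclusions.

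**What to change.** 1. In Table 2, add one short, fixed adverse-event question set, identical in both arms, to the existing REDCap forms at session 6, session 12, 3 months and 6 months. It could ask about new or worsened health or emotional problems since the last form, medical visits or emergency care, and distress the woman attributes to the study. Send it to all randomised women, including those who have stopped therapy, and offer it at withdrawal where the woman agrees.
2. Reword section 17.1 to cover events reported on these forms or in therapy, with a definition of an adverse event and a collection window running to the 6-month follow-up.
3. Name the existing team role that reviews the online answers and state how promptly. Without this, the new questions would sit on unattended forms.
4. In section 8.5, add a descriptive table of events by randomised arm, with form-elicited and spontaneously reported events shown separately.

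The cost is a protocol amendment, a few REDCap items, about one minute per form and some investigator review time. No new visit is needed. Women who leave the study entirely and decline the withdrawal questions will still be missed. The change is best made before follow-up begins, since events not asked about at the time cannot be reliably reconstructed.
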